8.4.8.2 Paternal Exposure

There is no restriction on fathering children or donating sperm during the study.

8.4.9 Medication Error, Drug Abuse, and Drug Misuse

8.4.9.1 Timelines

If a medication error, drug abuse, **or** drug misuse occurs during the study, then the investigator or other site personnel informs the appropriate AstraZeneca representatives within **1 calendar day**, ie, immediately but **no later than 24 hours** of when they become aware of it.

The designated AstraZeneca representative works with the investigator to ensure that all relevant information is completed within 1 (Initial Fatal/Life-Threatening or follow up Fatal/Life-Threatening) or 5 (other serious initial and follow up) calendar days if there is an SAE associated with the medication error, drug abuse, or misuse (see Section 8.4.7) and within 30 days for all other medication errors.

8.4.9.2 Medication Error

For the purposes of this clinical study a medication error is an **unintended** failure or mistake in the treatment process for an IMP that either causes harm to the participant or has the potential to cause harm to the participant.

The full definition and examples of Medication Error can be found in Appendix C4.

8.4.9.3 Drug Abuse

Drug abuse is the persistent or sporadic **intentional**, non-therapeutic excessive use of IMP for a perceived reward or desired non-therapeutic effect.

The full definition and examples of drug abuse can be found in Appendix C4.

8.4.9.4 Drug Misuse

Drug misuse is the **intentional** and inappropriate use (by a study participant) of IMP for medicinal purposes outside of the authorized product information, or for unauthorized IMP, outside the intended use as specified in the protocol and includes deliberate administration of the product by the wrong route.

The full definition and examples of drug misuse can be found in Appendix C4.

8.4.10 Medical Device Deficiencies

Medical devices are being provided for use in this study as the study intervention is supplied in prefilled syringes are being utilized to deliver the IMP under study. In order to fulfil regulatory reporting obligations worldwide, the investigator is responsible for the detection and documentation of events meeting the definitions of medical device deficiency that occur during the study with such medical devices.

The definition of a Medical Device deficiency can be found in Appendix E.

NOTE: Incidents and deficiencies fulfilling the definition of an AE/SAE will also follow the processes outlined in Appendix E of the protocol.

In this study any deficiency observed with a third-party medical device will be collected and reported to the manufacturer.

A medical device deficiency is an inadequacy of a medical device with respect to its identity, quality, durability, reliability, safety, or performance. Medical device deficiencies include malfunctions, use errors, and information supplied by the manufacturer.

The AstraZeneca medical device complaint report will be used to collect the deficiency.

8.4.10.1 Time Period for Detecting Medical Device Deficiencies

Medical device incidents or malfunctions of the medical device will be detected, documented, and reported during all periods of the study in which the medical device is used.

If the investigator learns of any medical device deficiency at any time after a participant has been discharged from the study, and such incident is considered reasonably related to a medical device provided for the study, the investigator will promptly notify the sponsor.

The method of documenting Medical Device Deficiency is provided in Appendix E.

8.4.10.2 Follow-up of Medical Device Deficiencies

Follow-up applies to all participants, including those who discontinue study intervention.

The investigator is responsible for ensuring that follow-up includes any supplemental investigations as indicated to elucidate the nature and/or causality of the deficiency.

New or updated information will be recorded on the originally completed form with all changes signed and dated by the investigator.

8.4.10.3 Prompt Reporting of Medical Device Deficiencies to Sponsor

Medical device deficiencies will be reported to the sponsor within 24 hours after the investigator determines that the event meets the protocol definition of a medical device deficiency.

In this study, deficiency observed with any of study treatment medical devices (benralizumab [Fasenra®]) will be collected and reported to the manufacturer using the form available on the Pharmacy manual (for more details please follow up Pharmacy manual).

The third-party medical device deficiency (Spirostik) will be reported by Investigator on the paper form as per the User Manual.

The sponsor will be the contact for the receipt of medical device deficiency reports.

8.4.10.4 SADE Reporting

NOTE: There are additional reporting obligations for device constituent deficiencies that are potentially related to SAEs that must fulfil the legal responsibility to notify appropriate regulatory authorities and other entities about certain safety information relating to device constituents being used in clinical studies.

- Any device constituent deficiency that is associated with an SAE must be reported to the sponsor within 24 hours after the investigator determines that the event meets the definition of a device constituent deficiency.
- The sponsor will review all device constituent deficiencies and determine and

document in writing whether they could have led to an SAE. These device constituent deficiencies will be reported to the regulatory authorities and IRBs/IECs as required by national regulations.

8.4.10.5 Regulatory Reporting Requirements for Device Deficiencies

The investigator will promptly report all medical device deficiencies occurring with any medical device provided for use in the study in order for the sponsor to fulfil the legal responsibility to notify appropriate regulatory authorities and other entities about certain safety information relating to medical devices being used in clinical studies.

The investigator, or responsible person according to local requirements (e.g., the head of the medical institution), will comply with the applicable local regulatory requirements relating to the reporting of medical device deficiencies to the IRB/IEC.

For further guidance on the definition of an SAE, see Appendix E of the CSP.

8.5 Overdose

For this study, any single dose of benralizumab greater than > 30 mg will be considered an overdose.

There is currently no specific treatment in the event of overdose of IP and possible symptoms of an overdose are not established.

- An overdose with associated AEs is recorded as the AE diagnosis/symptoms on the relevant AE modules in the eCRF and on the Overdose eCRF module.
- An overdose without associated symptoms is only reported on the Overdose eCRF module.

If an overdose on an AstraZeneca study intervention occurs in the course of the study, the investigator or other site personnel inform appropriate AstraZeneca representatives immediately, but **no later than 24 hours** of when he or she becomes aware of it.

The designated AstraZeneca representative works with the investigator to ensure that all relevant information is provided to the AstraZeneca Patient Safety data entry site within one or 5 calendar days for overdoses associated with an SAE (see Section 8.4.7) and within 30 days for all other overdoses.

8.6 Human Biological Samples

The collection and handling of biological samples should be conducted per site's local procedures. Samples should be stored in a secure storage space with adequate measures to protect confidentiality. For further details on Handling of Human Biological Samples see Appendix D.

8.6.1 Pharmacokinetics

Pharmacokinetic parameters will not be evaluated in this study.

8.6.1.1 Determination of Drug Concentration

Pharmacokinetic parameters will not be evaluated in this study. Therefore, the determination of drug concentration will not be conducted.

8.6.2 Immunogenicity Assessments

Immunogenicity assessments will not be conducted in this study.

8.6.3 Pharmacodynamics

Pharmacodynamic parameters will not be evaluated in this study.

8.6.3.1 Collection of Samples

Pharmacodynamic parameters will not be evaluated in this study. Therefore, no sample collection will be conducted for this purpose.

8.7 Human Biological Sample Biomarkers

8.7.1 Collection of mandatory samples for biomarker analysis

Biomarkers will not be evaluated in this study. Therefore, no mandatory sample collection will be conducted for this purpose.

8.7.2 Collection of Optional Biomarker Samples

Biomarkers will not be evaluated in this study. Therefore, no optional sample collection will be conducted for this purpose.

8.7.3 Other Study Related Biomarker Research

Other study related biomarker research will not be conducted in this study.

8.8 **Optional Genomics Initiative Sample**

Optional Genomics Initiative research will not be a part of this study.

8.9 Health Economics OR Medical Resource Utilization and Health Economics

Health Economics/Medical Resource Utilization and Health Economics parameters are not evaluated in this study.

9 STATISTICAL CONSIDERATIONS

9.1 Statistical Hypotheses

For the primary and secondary objectives, measures of mean within subject difference in FRI parameters (enumerated in Table 3) between weeks 0 and 13 the null hypothesis is a difference of 0, an assumption based on existing data described in Section 4.2 suggesting untreated participants are likely to exhibit stable or declining primary endpoint values over a similar (12 week) time period.

9.2 Sample Size Determination

Note: "Enrolled" means a participant's, or their legally acceptable representative's, agreement to participate in a clinical study following completion of the informed consent process. Potential participants who are screened for the purpose of determining eligibility for the study, but are not assigned in the study, are considered" screen failures", unless otherwise specified by the protocol.

9.3 **Populations for Analyses**

The following populations are defined:

Population/Analysis set	Description		
Enrolled	All participants who sign the informed consent form		
Randomly assigned to study intervention	NA (single-arm study)		
Evaluable	All participants who have completed three doses of investigational product, and have baseline and post-benralizumab treatment study evaluation (PROs, CT scans and spirometry tests) - the evaluable population.		
Primary analysis population	The portion of the evaluable population that did not have an acute asthma exacerbation nor lower respiratory tract infection during the study period will be the primary analysis population for the endpoints in this study.		
Baseline endpoints analysis set	Participants who have baseline measurements and who have had at least one dose of investigational product, irrespectively of whether they discontinued for reasons described in Section 7.1 will be included for analyses conducted on the study population who at least started treatment.		
Safety analysis setThe Safety analysis set consists of all participants who have receive one dose of investigational product.			

Table 8Populations for Analysis

9.4 Statistical Analyses

The statistical analysis plan will be finalized prior to Data Base Lock, and it will include a more technical and detailed description of the statistical analyses described in this section. This section is a summary of the planned statistical analyses of the most important endpoints including primary and key secondary endpoints.

9.4.1 General Considerations

All continuous variables (including FRI parameters, pre-BD FEV₁, pre-BD FVC, CCI) will be summarized using means, standard deviations and 95% ranges, or medians and inter-quartile ranges, depending on the distributions of the data. Mean changes from baseline in continuous variables will be reported, including asymptotic 95% confidence intervals and standard errors. Categorical data (e.g., CCI CCI CCI CCI CCI CCI asthma control category) will be summarized as the number and percentage among patients with non-missing data. Descriptive statistics will also be calculated for the data stratified by gender. Unless otherwise stated, all hypothesis tests are two-sided and all hypothesis tests will be performed at a 5% significance level. Analyses will be carried out for overall patients and subgroups as specified in Section 9.4.4. Data may be log-transformed prior to analysis to reduce skewness of FRI parameters.

9.4.2 Efficacy

9.4.2.1 Primary Objectives

For the primary objective, a paired *t*-test will be used to determine if there is a significant difference between the mean of untrimmed total mucus volume at TLC at week 0 vs week 13, irrespective of patient characteristics.

Secondary analysis of the primary endpoint (untrimmed total mucus volume at TLC) will be a mixed-effects model to incorporate the repeated measurements (corresponding to the different lobes) for each subject. The outcome of change from baseline in the primary endpoint at week 0 vs week 13 per lobe will be modelled in terms of a fixed effect for lobe and a patient-level random effect to estimate the heterogeneity across lobes. Adjustment will be made for baseline mucus volume per lobe. The fitted model will estimate the average change from baseline in mucus volume at week 0 vs week 13 per lobe.

9.4.2.2 Secondary Objectives

For the secondary objective 1, univariate paired *t*-tests and mixed effects modelling will be used to assess whether there are statistically significant differences in the means of secondary FRI endpoints (untrimmed total mucus plugs score at TLC, untrimmed total air trapping at FRC, trimmed distal iVaww at TLC, trimmed distal siVaw at TLC and FRC, and untrimmed total iVlung at TLC and FRC) at week 0 vs week 13, unadjusted for patient characteristics.

Secondary analysis of each secondary endpoint will be a mixed-effects model to incorporate the repeated measurements (corresponding to the different lobes) for each subject. The model will estimate the average change from baseline in secondary endpoint at week 0 vs week 13 per lobe, after accounting for the baseline measurement of the secondary endpoint per lobe and heterogeneity across lobes.

For secondary objective 2, a scatter plot will be used to display values of imaging endpoints (primary and secondary FRI parameters) and conventional lung function measures (pre-BD FEV₁ and pre-BD FVC response) at week 0, to get a first indication of the relationship between endpoints at baseline. Spearman's rank correlation coefficients will describe the strength of the association between two endpoints. Pearson correlation will also be used for linear relationships. Regression models will be used to estimate the average increase in imaging endpoints per unit increase in conventional lung function measures, with 95% confidence intervals.

For secondary objective 3, a scatter plot will be used to display changes from baseline at

week 13 in imagine endpoints (primary and secondary FRI parameters) against changes from baseline at week 13 in conventional lung function measures (pre-BD FEV₁ and pre-BD FVC response). Both Spearman's rank and Pearson correlation coefficients will describe the strength of the association. If changes from baseline in conventional lung function measures at week 13 are related to baseline values, as indicated by fitted regression models, correlation coefficients will be reported per subgroup defined by baseline value.

A linear regression model for imaging endpoints will be fitted, consisting of a binary explanatory variable (corresponding to week 13). The regression coefficient for time will estimate the change from baseline (week 13 vs week 0) in the imaging endpoint. The model will be fitted with and without the inclusion of the change from baseline in pre-BD FEV₁ and pre-BD FVC as individual covariates. Estimated regression coefficients for time from the unadjusted and adjusted models will be compared, to indicate whether the change from baseline in the imaging parameter is explained by changes in pre-BD FEV₁ and pre-BD FVC. Estimated regression coefficients for changes in pre-BD FVC will be reported, to quantify the average change in each imaging endpoint for every one percent increase in pre-BD FEV₁ and pre-BD FVC.

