3.2.1.5 Secondary Analysis of Primary Endpoint

For the secondary analysis of the primary endpoint a mixed-effects model will be employed to incorporate the repeated mucus volume measurements (corresponding to the different lobes) for each subject. The fitted model will provide estimates of the average change from baseline in mucus volume per lobe, with lobe as a fixed effect and a patient-level random effect to estimate the heterogeneity across lobes. Adjustment will be made for the baseline value of mucus volume.

Equation 1 The mixed-effects model will be as follows:

$$y_{ij} = \beta_0 + \beta_{1j}X_{ij} + \beta_2(baseline)_{ij} + b_{0j} + \varepsilon_{ij}$$

where

• y_{ij} represents change from baseline in mucus volume for subject *i* lobe *j*

- β_0 is the intercept
- β_{1j} is the coefficient for lobe *j*, estimating the average change from baseline in mucus volume for lobe *j*
- X_{ij} is an indicator of whether the mucus volume measurement for subject *i* corresponds to lobe *j*
- β_2 is the coefficient for baseline mucus volume
- $(baseline)_{ij}$ is the baseline mucus volume value for subject *i* corresponding to lobe *j*.
- b_{0i} is the random effect for the *i*th subject
- ε_{ij} is the residual error term

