3.2.2.3 Handling of Dropouts and Missing Data

The analysis populations will only include participants who have completed three doses of study intervention and have baseline and post-benralizumab treatment study evaluation (PROs, CT scans, and spirometry tests). To that end, participants withdrawing before Week 13 and participants with one of the two FRI measurements missing will not be included in the analysis.

3.2.2.4 Primary Analysis of Secondary Endpoint 1

For each secondary FRI endpoint listed in Table 2, a paired t-test will be used to assess whether there is a statistically significant difference in the mean value at Week 0 versus Week 13, without adjustments for participant characteristics. Data will be log-transformed prior to analysis if there is evidence of skewness.

3.2.2.5 Secondary Analysis of Secondary Endpoint 1

For the secondary analysis of the secondary endpoint, a mixed-effects model will be employed to incorporate the repeated measurements (corresponding to the different lobes) for each subject. The fitted model will be provide estimates of the average percent change from baseline per lobe, with lobe as a fixed effect and a patient-level random effect to estimate the heterogeneity across lobes. The model will adjust for the baseline value of the secondary endpoint. The model will take the same form as described in Equation 1, but with "mucus volume" replaced by the secondary outcome of interest.

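### The lobe models evaluate every lobe's change at one shared baseline, so the per-lobe figures are not the average changes the plan says they are

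*Protocol*

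**What the plan says.** **Protocol.** Section 9.4.2.1 plans a mixed model on lobe-level data as the secondary analysis of the primary endpoint, to estimate the mean change in mucus volume in each lobe: "Adjustment will be made for baseline mucus volume per lobe". Section 9.4.2.2 plans the same for each secondary endpoint, "after accounting for the baseline measurement of the secondary endpoint per lobe and heterogeneity across lobes".

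**SAP 3.2.1.5.** The model is described "with lobe as a fixed effect and a patient-level random effect to estimate the heterogeneity across lobes", and "Adjustment will be made for the baseline value of mucus volume". In Equation 1 the baseline term is that lobe's own value, uncentred. It has a single coefficient β2, which "is the coefficient for baseline mucus volume", and there is no lobe-by-baseline term. The lobe coefficient is defined as "estimating the average change from baseline in mucus volume for lobe" j.

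**SAP 3.2.2.5.** For the secondary endpoints, "The model will take the same form as described in Equation 1", and "The model will adjust for the baseline value of the secondary endpoint". Here and in Table 5 the outcome is percent change. Protocol 9.4.2.2 and SAP Table 3 say change.

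**Related rules.** Skewed data are log-transformed (SAP 3.2.1.4 and 3.2.2.4). Addendum 2.11.3 makes this log(x+1) for mucus volume and names only specific airway volume and airway wall volume as other candidates. Addendum 2.9 settles the covariance structure. No section says at which baseline the lobe means are evaluated.

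**The concern.** A model with lobe effects and one common baseline slope compares lobes at the same baseline value. The five lobes differ anatomically in size and may differ in mucus load. A middle lobe evaluated at the baseline of an average lobe is not a lobe that any participant has. Retest noise alone makes the slope of change on baseline negative, and so does an effect proportional to load. The adjusted lobe figure then departs from that lobe's actual mean change.

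At stake are the lobe-specific results of the planned secondary analyses. Falls or rises could be reported, and called significant if tested at the plan's two-sided 5% level, in lobes that did not change. Real differences between lobes could also be flattened. With a single arm there is no treatment contrast that gains from moving lobes to a common baseline.

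**Working it through.** The plan states no lobe-level figure to reproduce. The sample size of 29 (Protocol synopsis) serves only as n in the simulations.

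**1. Algebra.** With complete lobe data, the lobe fixed effects force residuals to sum to zero within each lobe. Therefore

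estimate_j(c) = mean change_j − b × (mean baseline_j − c).

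This equals mean change_j only if b = 0 or mean baseline_j = c. A single c can serve all lobes only if they share the same mean baseline. Taking Equation 1 literally (intercept plus lobe effect, baseline term at zero) gives c = 0. Least-squares means would by default use the overall mean baseline.

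**2. Lung volume, no true change.** Assumptions, none in the documents: lobe means RUL 1.0, RML 0.45, RLL 1.3, LUL 1.15, LLL 1.2 L (overall 5.10/5 = 1.02 L); patient CV 20%, lobe CV 10%; n = 29; random patient intercept. At 5% shared (inflation) noise and 4% lobe noise the simulated slope is about −0.105:
- RML at the overall mean: 0.105 × (0.45 − 1.02) = −0.060 L
- RLL at the overall mean: 0.105 × (1.30 − 1.02) = +0.029 L
- At c = 0: from 0.105 × 0.45 = +0.047 L to 0.105 × 1.30 = +0.137 L, a rise in every lobe

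Simulated results at the overall mean baseline (ranges are over repeated sets of runs):

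| Shared / lobe noise | RML | Significant | RLL | Significant |
|---|---|---|---|---|
| 0% / 2% | −5 to −6 mL | about 7% | | |
| 2% / 2% | −12 to −13 mL | 23–24% | | |
| 5% / 4% | −61 to −63 mL | 54–57% | +27 to +29 mL | 23–26% |
| 8% / 6% | −123 mL | 76–83% | +60 mL | 47–50% |

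**3. Different assumptions.** Lobe means 1.05, 0.50, 1.35, 1.20, 1.20 L (overall 1.06 L), between-patient CV 25%, between-lobe correlation 0.6. At 5% lobe and 5% shared noise:
- b = −0.086, RML −0.049 L (39% significant), RLL +0.025 L (21%).
- With unstructured covariance, RML −0.050 L (62%).
- At c = 0, rises of 0.04 to 0.12 L.

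Across noise settings RML ranged from −0.004 to −0.117 L. With equal lobe sizes the displacement at the overall mean vanished (within about 0.002 L).

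**4. Other scales.** With percent change as outcome at 5%/4% noise under the step 2 assumptions, RML is about −4.2% (42% significant) and RLL +2.7% (31%). The 62 mL is about 14% of a 0.45 L lobe, so the relative displacement is roughly a third as large on the percent scale. Step 3 gives −3.4% and +2.5%, against raw means near +0.5%. On the log scale, step 3 gives RML −0.050 and RLL +0.021.

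**5. Mucus halved in every lobe.** Assumed baselines 0.3, 0.2, 1.5, 1.0, 2.0 (mean 1.0), so b = −0.5.
- Untransformed, at the overall mean: −0.5m_j + 0.5(m_j − 1.0) = −0.5 in every lobe. Simulation gave about −0.51 throughout, against true changes of −0.16, −0.10, −0.76, −0.52 and −1.01. At c = 0 the same arithmetic gives 0 in every lobe.
- Under log(x+1): reported −0.22 to −0.28, against raw −0.10 to −0.40.
- Under a pure log: halving is ln 0.5 = −0.69 in every lobe, and the model returns it.

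**6. Baseline centred within lobe.** Estimates equal the raw mean changes: within 4 mL of zero in step 2 and 0.003 L in step 3. The 62% in step 3 falls to 4%. With only a random intercept and equal residual variances, centring still corrects the estimates, but rejection rates were 0% for RML and 13% for RLL. Correct error rates also need lobe-specific variances.

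**The case against.** - **It is an estimand choice.** The protocol says the lobe change accounts for baseline, and comparing lobes at equal load is a legitimate conditional question. But Equation 1 defines the lobe coefficient as that lobe's average change, and the model does not deliver that.
- **The model itself is sound.** This stands. Because lobe is already a fixed effect, centring within lobe leaves the fit unchanged. Only the baseline at which lobes are evaluated moves, so the defect lies in what is reported.
- **Falls in small lobes and rises in large ones.** A reader might infer that the plan as written produces this pattern. That requires least-squares means at the overall mean baseline, which the plan never names. The literal reading gives rises in every lobe for untransformed volumes.
- **The planned scales soften it.** This stands in part. The percent scale shrinks the displacement, log(x+1) compresses lobe differences rather than erasing them, and a pure log would handle proportional halving. Lung volume is not among the addendum's candidates for transformation.
- **Noise may be low.** Protocol 4.2 cites studies finding little variation in these imaging measures without intervention. At 2% lobe noise with no shared noise the displacement is about 6 mL and the error rate near nominal.

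**Conclusion.** The concern holds for lobe-specific results. The lobe figures are not the average changes claimed unless b is zero or the lobe's mean baseline equals the evaluation baseline. That part is algebra. The size is conditional, because lobe sizes and retest noise are assumed: for the middle lobe's lung volume with no true change, from about −6 mL (near-nominal error) through about −62 mL (significant in roughly 55% of runs) to about −123 mL. On the SAP's percent scale it is about −4% in the middle case.

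It applies to endpoints whose lobe means differ: mucus volume, iVlung, iVaww, and the iVaw endpoints that Addendum 1.4 substitutes for siVaw. A reader might extend it to every secondary endpoint, but it has not been shown for siVaw, which is size-normalised, or for air trapping, whose data specification is redacted. Nor does it undermine the main result: the primary paired t-test, the paired t-tests on secondary endpoints and the five-lobe average at the overall mean baseline are unaffected. It should be corrected, but it does not threaten the primary conclusion.

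**What to change.** In Protocol 9.4.2.1 and 9.4.2.2 and SAP 3.2.1.5 (Equation 1) and 3.2.2.5:

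1. Enter baseline as baseline_ij minus the mean baseline of lobe j, computed on the analysis scale after any transformation.
2. Report lobe means with 95% CIs from a no-intercept or least-squares-means coding, so that each lobe is evaluated at its own mean baseline. With complete lobe data these equal the raw mean changes; with the incomplete scans foreseen in Addendum 2.14 the equality need not be exact.
3. Reconcile percent change (SAP 3.2.2.5 and Table 5) with change (Protocol 9.4.2.2 and SAP Table 3).

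If the unstructured covariance in Addendum 2.9 does not converge, prefer a fallback with lobe-specific variances.

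Leaving baseline out gives the same point estimates with complete data but loses the residual adjustment, so it is an alternative rather than an equivalent.

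The cost is one derived variable and a sentence in each section, with no change to data or design.
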